Outcome(s):	The German S3 Guidelines for the treatment of depression in children and youth define the background treatment for all participants. All clinical partners will be trained and monitored accordingly. The primary outcomes are the (continuous) Children's Depression Rating Scale-revised (CDRS-R) total score and the (dichotomous) rates of recovery defined by the absence of pMDD for >4months at 36 weeks, as well as response and remission rates at 12 and 36 weeks. Inflammatory mediators in serum using immunoassays, red blood cell omega-3, 6, 9 and trans fatty acids using gas chromatography (GC) and bioactive lipid mediators (e.g. E-series resolvins) using mass spectrometry (LC-MS/MS) will be measured as potential response predictors. Adverse events/ harm endpoints (in particular suicidality) will be coded using MedDRA. Adherence measurements are pill counts, as well as n-3 EPA/DHA levels across the study. Blood samples will be taken at study entry, week 12 and 36.
Study design:	A Swiss, multicentre, randomised, double-blind, placebo-controlled clinical trial.
Inclusion / Exclusion criteria:	The study aims to randomize a sample of 220 individuals aged 8 - 17 years, who are in- or outpatients of a participating centre and have a present primary diagnosis of major depression disorder with depressive symptoms of at least moderate severity. Participants with pre-existing neurological or medical conditions likely to be responsible for the depressive symptoms or other psychopathological diagnoses are excluded.
Measurements and procedures:	The study design incorporates a 1-2week screening, a 7 -10days placebo lead-in and a 36week double-blind placebo-controlled treatment phase. The severity of the depression and psychosocial functioning will be assessed at baseline and at each study visit (twice in the acute phase and twice in the maintenance phase) using a variety of different questionnaires and rating scales. Cognitive testing and biological markers (blood, urine and saliva) will be sampled at baseline and at 12 and 36 weeks. Adherence to the study will be checked by pill count at each study visit and PUFA level measurements in red blood cell membranes at baseline, 12 and 36 weeks will be performed.

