8.1.1 Experimental Intervention

Treatment A (Omega-3 fatty acid)

- Omega-3 fatty acids
- Approx.168 mg EPA and 84 mg DHA per capsule
- Children < 13 years of age are advised to take 3 capsules resulting in approx. 500 mg EPA and 250 mg DHA per day
- Teenagers > 13 years of age are advised to take 6 capsules resulting in approx. 1000 mg EPA and 500 mg DHA per day.
- In addition, the capsules also contain mixed tocopherols and d-alpha-tocopherol (vitamin E) derived from soy oil.
- They also contain 3mg of orange oil.

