8.1.2 Control Intervention

Treatment B (placebo)

- 418 mg medium chain triglycerides
- In addition, the capsules also contain mixed tocopherols and d-alpha-tocopherol (vitamin E) derived from soy oil.
- The capsules contain about 1.6mg of fish oil and 3mg of orange oil
- As in the active treatment, children < 13 years of age are advised to take 3 capsules and teenagers > 13 years of age are advised to take 6 capsules, respectively.

Burgerstein will produce specially manufactured child capsules as study medication that can easily be swallowed by children. Further information can be found in the Investigator's Brochure.

[figure not shown]

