8.4 Compliance with Study Intervention

The investigator will perform pill counts at each study research visit and patients will complete the MARS-D questionnaire (in <13 year olds, with parents support) -regularly, or as advised by the research psychologist. Red blood cell omega-3 fatty acids measurements will be used to monitor compliance, a commonly used method in previous trials [180]. On a study team level, regular meetings with the omega-3-pMDD study side teams will address site specific adherence issues (e.g. the postdoctoral study coordinator or one of the applicants will join a clinical meeting where most clinicians are present to address questions around the trial).

Non-compliance is defined as the discontinuation of taking the study medication for longer than three days out of seven days in two consecutive weeks, regardless of the circumstances, prior to completion of the trial. If a patient fulfills criteria of non-compliance, the participation will be terminated. The data will still be included into statistical analyses as the number of drop outs due to cessation/non-compliance is also an outcome measure between the groups. The reason for a subject discontinuing the study will be recorded in the eCRF.

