8.8 Study Drug Accountability

Subjects will be asked to return any unused medication to the site. Accountability and subject adherence will be assessed by maintaining drug dispensing and return records. Adherence to the study medication will also be monitored by self-report, and the measurement of the omega-3 to omega-6 ratio in blood at screening and after six months will provide a measure of drug compliance (see above)

A Drug Accountability Log must be kept current and should contain the following information:

- the identification of the subject to whom the medication was dispensed
- the date[s], quantity of the medication dispensed to the subject
- the date[s] and quantity of the medication returned by the subject

This inventory must be available for inspection by the monitor. The shipping, receipt, returning and destruction will be tracked and documented in line with Good Clinical Practice (GCP) guidelines.

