9.2.2.4 Biological outcome measures

Blood sampling procedures will be described in a Standard Operating Procedure 'Blood Sampling' (jointly developed by [name]. [name] and [name]. [name] together with the main applicant). Blood samples will be drawn from pMDD subjects after enrolment, at week12 and week36 to assess routine laboratory parameters.

- Haemoglobin
- Haematocrit
- Leucocytes
- Thrombocytes
- Thyroid (TSH only)
- Liver function test (ALAT, ASAT)
- hsCRP
- Ferritin

The remaining blood will be stored for PUFAs (omega-3, 6 and 9 and trans fatty acids), bioactive lipids (e.g. E-series resolvins), immune parameters (including but not restricted to interferon- γ , interleukin (IL)-1 α , IL-1RA, IL-5, IL-6, IL-10, IL12p40, IL-15, IL-18 and tumour necrosis factor- α , as well as leptin and adiponectin), and for the tissue repository. In addition, 2.7ml blood will be drawn in order to assess mitochondrial metabolism.

Except for hsCRP (a stratification variable) all markers of prediction will be measured at the end of trial after completion of the final visit of the last patient (to prevent unblinding), except of the baseline data that might be used in the context of planned add-on projects that will be submitted as amendments (e.g. sleep project, imaging project). Altered levels of these parameters have been shown in MDD and other disorders, and may predict both the course of the illness and how levels of bioactive lipids, and immune parameters are related to both: a.) if these blood parameters are able to serve as potential biomarkers that may predict clinical outcome and b.) if these blood parameters are associated with psychopathology and illness course.

Since multiple studies are currently investigating biomarkers in MDD, serum, lymphocytes, erythrocyte, platelets and DNA will be stored after the end of the study to measure potential novel biomarkers. Genetic and epigenetic markers of interest (e.g. FADS haplotypes) include but are not restricted to genes relevant for bioactive lipid metabolism. The establishment of the genetic tissue repository is part of the project but will be financed separately, as this is not core to the proposed IICT. Ethics approval for the generation of the tissue repository has been granted (Applicant Prof. [name], BASEC-Nr. 2016-00101).

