- Furthermore, we plan to reanalyze the IIT sample according to the PUFA baseline status. In particular we want to compare participants with a omega-3 index <3 compared to those with an omega-3 index $>3/5$ or 8, as increasing evidence suggest that in particular those with a low omega-3 index may benefit from omega-3 supplementation.
- Furthermore, we plan to investigate the influence of inflammatory mediators as response predictors [63].
- Finally we will reanalyze the ITT sample using compliance data (pill count, rbc EPA/DPA change levels, MARS score) to compare fully compliant study participants with partially compliant and non-compliant patients.
- More exploratory will be the analysis of EPA metabolites (HETE; E-series resolvins, prostaglandine, leukotriene) that will be measured in the context of a PhD project as potential predictors of omega-3 fatty acid response.

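### The compliance reanalysis in Protocol 11.4.1 grades both arms partly on red-cell fatty-acid change, which cannot track capsule intake on placebo, so compliance level can be confounded with arm to a degree set by an unstated rule

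*Protocol*

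**What the plan says.** Protocol 11.4.1 proposes a reanalysis by compliance in the ITT population, "using compliance data (pill count, rbc EPA/DPA change levels, MARS score) to compare fully compliant study participants with partially compliant and non-compliant patients". The same section defines the ITT sample as everyone randomised. There are three measures and three levels, but nothing on thresholds, on how the measures combine, on missing red-cell values (9.2.2.4 makes the research blood samples optional), or on whether the comparison is made within or across arms. The marker is written EPA/DPA here and EPA/DHA in the synopsis.

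Other sections also treat blood fatty acids as an adherence measure without limiting them to one arm. Section 8.4 says "Red blood cell omega-3 fatty acids measurements will be used to monitor compliance". Section 8.8 says "the measurement of the omega-3 to omega-6 ratio in blood at screening and after six months will provide a measure of drug compliance".

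On capsule content, 8.1.1 gives the active product as "Approx.168 mg EPA and 84 mg DHA per capsule". For placebo, 8.1.2 lists medium chain triglycerides as the filling and adds "The capsules contain about 1.6mg of fish oil and 3mg of orange oil". Section 3.6 notes that this filling has no unsaturated fatty acids.

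**The concern.** A compliance measure used in both arms has to respond to intake in both arms. Red-cell EPA/DHA can rise with capsule intake only where the capsules contain EPA and DHA. On placebo, a rise reflects diet, off-trial omega-3 or assay noise. Whatever weight the marker receives therefore ties compliance level to treatment arm.

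Two things are at stake. A pooled comparison of compliance levels could partly repeat the arm comparison and be read as an effect of adherence. If the marker is decisive, an arm comparison within the top level would also set adherent omega-3 participants against a small placebo group selected for outside omega-3 intake or noise. Either result would depend on a classification choice that the protocol leaves open.

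**Working it through.** **1. Stated dose.** With 168 mg EPA and 84 mg DHA per capsule, six capsules give 6 × 168 = 1008 mg EPA and 6 × 84 = 504 mg DHA. This reproduces the stated "resulting in approx. 1000 mg EPA and 500 mg DHA per day". Three capsules give 504 mg and 252 mg, matching the stated dose for younger participants.

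**2. Placebo supply.** Six placebo capsules hold 6 × 1.6 = 9.6 mg of fish oil, only part of which is EPA or DHA. Six active capsules hold 1008 + 504 = 1512 mg. The ratio is at most 9.6 / 1512 = 0.63%. With three capsules it is 4.8 / 756 = 0.63%.

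**3. Effect of the unstated rule.** The following inputs are assumptions, not figures from the documents:
- 1:1 arms, with true full adherence of 60–80% in both.
- Pill count positive in 95% of adherent and 10% of non-adherent participants.
- MARS positive in 90% and 20% respectively.
- A red-cell rise detected in a proportion s = 80–95% of adherent omega-3 participants and f = 5–20% of everyone else.
- The measures are independent given true adherence.

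With p, m and r the chances of a positive pill count, MARS and red-cell result, the chance of being labelled fully compliant is:
- all three required: p·m·r
- two of three: p·m + p·r + m·r − 2·p·m·r
- one measure alone: p or r

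Worked case, all three required, adherence 0.8, s = 0.8, f = 0.2:
- Omega-3 arm: 0.8 × (0.95 × 0.90 × 0.80) + 0.2 × (0.10 × 0.20 × 0.20) = 0.548
- Placebo arm: 0.8 × (0.95 × 0.90 × 0.20) + 0.2 × 0.004 = 0.138
- Omega-3 share of the fully compliant group: 0.548 / (0.548 + 0.138) = 0.80
- Omega-3 share of the rest: 0.452 / (0.452 + 0.862) = 0.34

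Suppose omega-3 has a true SMD of 0.4 (the smaller effect in SAP 6.1) and adherence itself has no effect. A pooled contrast of fully compliant participants against the rest, unadjusted for arm, then shows 0.4 × (0.80 − 0.34) = 0.18, all of it spurious.

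Over the full range of assumptions:

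| Rule for fully compliant | Adherent placebo participants who qualify | Omega-3 share of that group | Spurious SMD |
|---|---|---|---|
| Pill count alone | 95% | 50% | 0 |
| Two of three | 86–88% | 52–53% | 0.02–0.05 |
| All three | 4–17% | 80–95% | 0.16–0.27 |
| Red-cell change alone | 5–20% | 74–94% | 0.15–0.30 |

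**4. A second model of the marker alone.** Assume 80% adherence, a rise of D = 2, 3 or 4 SD in adherent omega-3 participants and a cut at D/2.
- Placebo above the cut: 1 − Φ(D/2) = 0.159, 0.067, 0.023
- Omega-3 above the cut: 0.8·Φ(D/2) + 0.2·(1 − Φ(D/2)) = 0.705, 0.760, 0.786
- Omega-3 share: 0.82, 0.92, 0.97

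Taken together, the rules that require the marker or use it alone give 74–97%.

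**5. Sampling times.** The synopsis states "Blood samples will be taken at study entry, week 12 and 36". Sections 6.1 and 9.2.2.4 agree on weeks 12 and 36, and the week-24 visit in 9.3.5 mentions no blood. The six-month sample in 8.8 matches no scheduled draw.

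**The case against.** The strongest reply is that no rule exists, so no misclassification has been specified. A placebo participant with a full pill count and a good MARS score satisfies two of three measures and might be graded fully or partially compliant. Under a two-of-three rule the distortion is slight, and an analysis within arms would remove it. This stands. A reader might infer that adherent placebo participants will be classed as non-compliant, but no section says so; they can be misclassified, depending on the rule.

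Second, nothing decisive uses the marker. The non-compliance definitions in Protocol 8.4 (days without study medication) and in the SAP's missing-data section (less than 60% of pills taken) rest on capsule intake alone. The per-protocol sensitivity analysis in SAP 7.1.2 names no blood measure. The primary model uses the omega-3 index only as a baseline covariate. This also stands.

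Third, outside omega-3 intake is limited by the exclusion of prior regular supplementation (7.1.2) and by the withdrawal criterion for daily supplementation (7.4). That reduces one source of false positives on placebo but does not make the marker respond to placebo capsules.

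A reader might also infer from 8.4 that red-cell results would be seen during the trial and reveal allocation. The documents do not support that. Section 9.2.2.4 says that, hsCRP apart, "all markers of prediction will be measured at the end of trial after completion of the final visit of the last patient (to prevent unblinding", with an exception for baseline data. The synopsis counts red-cell fatty acids among those predictors, and 11.4 places all analyses except baseline data after database closure. Section 8.4 needs clarifying; it does not show a breach of the blind.

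**Conclusion.** The concern holds in a limited form. That red-cell change carries essentially no information on placebo capsule intake follows directly from the stated contents (at most 0.63% of the active amount). Section 11.4.1 nevertheless applies it to the whole ITT sample. How far compliance level becomes a proxy for arm depends on the missing rule and on assumed accuracies: an omega-3 share of 74–97% in the fully compliant group if the marker is required or used alone, 52–53% under two of three, and 50% with pill count alone. The spurious SMDs further assume a true effect of 0.4, no effect of adherence, and pooling without adjustment for arm.

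The consequence is confined to a supplementary reanalysis. It should not be read as a threat to the primary, confirmatory or safety results. It still deserves correction. Section 11.4 says an SAP will cover the planned a priori analyses, but the SAP restricts itself to efficacy and safety and does not include this one. Of the two documents, 11.4.1 is therefore the only specification, and a measure that works alike in both arms is already being collected.

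**What to change.** - **Protocol 11.4.1, or the later analysis plan that takes up this reanalysis:** grade compliance in both arms by pill count and MARS-D only, with cut-offs and the combination rule stated. Use red-cell change solely as an exposure measure within the omega-3 arm and, on placebo, as a check for off-trial omega-3 intake. Reconcile EPA/DPA with the synopsis's EPA/DHA.
- **Protocol 8.8:** reconcile the six-month sample with the scheduled week-12 and week-36 draws.
- **Protocol 8.4:** state, consistently with 9.2.2.4 and 11.4, that post-baseline red-cell results are read only after the trial ends. This is a clarification.

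The cost is wording only, with no new data. The one small loss is that the biomarker no longer contributes to the two-arm compliance grading.

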11.4.2 Primary Analysis

The continuous primary outcome measure is the CDRS-R total score. We will analyze the primary efficacy measure using a joint model containing a linear random effects regression model (similar to the TADS study [253, 254]) and a time-to-event model to account for missing information due to additional antidepressant use. Random regression in an ITT sample permits estimation of changes in continuous repeated measures in the presence of missing data on both a population and participant-specific level without necessitating last observation carried forward or exclusion of participants because of missing data. We will model the impact of treatment on outcome as a linear function of fixed effects for treatment, time (defined as the natural log of days since baseline + 1) and treatment-by-time interaction and random effects for participant and clinical site. Under the assumption of random intercepts and slopes for each patient, the overall and treatment group-specific rate of change for the 2 treatment groups for the primary CDRS-R outcome will be examined. A comparison on treatment slopes (linear trends with time) will then be conducted.

11.4.3 Secondary Analyses

Important CDRS-R-related outcome measures include response and remission. Remission is defined as a CDRS total score <28 and response is defined as a 30% drop in CRDS total baseline score (post placebo lead in). Participants using additional antidepressants, days on trial before the additional antidepressant, KIDscreen-CAT-27, and DIKJ will also be analyzed. Supportive endpoints include the number of days in the hospital and the amount of outpatient service use. For analysis details related to secondary and supportive outcomes of the primary trial reporting, please see the separate Statistical Analysis Plan document.

For further secondary outcomes, we will apply the same statistical strategy as for the primary outcome measures. Analysis will include changes in overall and subscores of the in chapter 9.2 listed secondary outcome instruments. We will analyze CDRS-R subscores, DIKJ, BHS, BAI, SIQ-Jr, IES-27, KIDscreen-CAT-27, PSS-10, and Resilience Scale scores and compare them between the treatment groups.

Furthermore, we'll run the following analyses to test our secondary working hypotheses:

- **WH3a:** We will test the effect of inflammatory mediators on the efficacy of omega-3 treatment by introducing an additional continuous factor (ratio between pro- and anti-inflammatory markers) into the linear regression model described in 11.4.2.
- **WH3b:** We will calculate an omega-3 index based on red blood cell Omega-3 fatty acids content and introduce an additional binary factor (n-6/n-3 Omega ratio < 3 vs. n-6/n-3 Omega ratio > 5) into the linear regression model described in 11.4.2.
- **WH3c:** We will test whether direct metabolites of EPA are a strong predictor of Omega-3 fatty acids by introducing additional continuous factors (levels of HETEs and E-series-resolvins at baseline) into the linear regression model described in 11.4.2
- **WH4a:** We will test association between pro-inflammatory state and depressive symptoms by calculating Pearson's correlation coefficient or Spearman's correlation coefficient between the severity of symptoms at baseline and the ratio between pro- and anti-inflammatory markers. The same procedure is also applied to omega-6/3 ratio and omega-3 index. To test whether normalization of these parameters will correlate with improvements in depression scores we'll run a linear regression model with depression scores as dependent, and time and pro-inflammatory state, increase in omega-6/3 and omega-3 index as independent variables.
- **WH4b:** We will calculate Pearson's correlation coefficient or Spearman's correlation coefficient of omega-3 index with SIQ-Jr scores depending on the distribution of the data.
- **WH4c:** As above, we will calculate either Pearson's correlation coefficient or Spearman's correlation coefficient (depending on the distribution of the data) between omega-3 index and scores on the IES-27 and overall psychopathology scores.
- **WH4d:** We also test correlations between levels of Omega-3 fatty acids with salvia cortisol, F2 isoprostanes and Connor-Davidsons Resilience Scale scores by

calculating Pearson's correlation coefficient or Spearman's correlation coefficient, respectively.

- **WH5a:** In order to compare treatment groups regarding occurrence of SUSARs, we will run a two proportions z-Test. Differences in suicidal ideation scores are tested by independent t-Test (for normal distributed data) or Mann-Whitney-U-Test (for non-normal data).

The analyses will be performed after closure of the database. The trial statisticians will perform all a-priori defined statistical analyses according to the statistical analyses plan. All other clinical outcome analyses will be declared as post-hoc analysis.

Future analysis based on the BioBank or other add on projects will be subject of an own protocol with separately formulated hypotheses that will be approved the appropriate authorities.

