5.2 Secondary Outcomes

WH 2a – We hypothesize that more pMDD patients in the placebo group will be put on antidepressant medication compared to the Omega-3 fatty acids group.

WH 2b – We hypothesize that the Omega-3 fatty acids group will achieve a higher level of functioning (a higher CGAS score) and a better quality of life (overall and within the five dimensions as assessed with KIDscreen-CAT -27) compared to the placebo group.

WH 2c – We hypothesize that the Omega-3 fatty acids group will spend fewer days in hospital and will have a lower outpatient service use (measured with the attrition check list) compared to the placebo group also resulting in a reduction in overall costs (calculated via TARMED points).

WH 2d – We hypothesize that the overall retention rate will be higher in the Omega-3 fatty acids group compared to the placebo group (or, in other words the placebo group will have more and earlier drop outs due to lack of efficacy). This hypothesis will be tested by two means: 1.) in the ITT sample independent if they received an antidepressant in the due course of the trial, as well as 2.) in a modified ITT sample, where those subjects that are put on an antidepressant will be considered as drop-outs from the day they received the first dose of an antidepressant.

WH 3a – Based on the recent meta-analysis [62] showing increased inflammatory mediators in adult MDD, we assume that at least 50% of participants will have a baseline increase of inflammatory mediators (in particular hsCRP, IL-1, IL-6) and a decrease of anti-inflammatory markers (IL-10). Based on a recent Omega-3 fatty acids treatment study in adult MDD [63], we hypothesize that Omega-3 fatty acid response will be predicted by the ratio between pro- and anti-inflammatory markers.

WH 3b – Based on the meta-analysis by Lin et al [54] as well as the study of Potalla et al [61] in pMDD, we hypothesize that about 80% of participants with pMDD will have a reduction in red blood cell Omega-3 fatty acids content, in particular EPA and DHA (used to calculate the Omega-3 index® [207, 208]). We hypothesize that those with an omega-3 index® <4 at baseline will benefit more from Omega-3 fatty acids treatment, whereas those with an omega-3 index >5 (approx. 20%) will not show a marked benefit from Omega-3 fatty acids treatment. We further hypothesize that a high n-6/n-3 Omega ratio at baseline will be associated with a better response to Omega-3 fatty acids.

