WH 3c – We hypothesize that low levels of direct metabolites of EPA, in particular HETEs and the E-series-resolvins (RvE1 & 2) will be a strong predictor of Omega-3 fatty acids response.

WH 4a – Based on the meta-analysis of Lin et al [54], we hypothesize that severity of depressive symptoms will be associated with a pro-inflammatory state, as well as an increase in omega-6/3 ratio and a decrease in omega-3 index. Normalization of these parameters will correlate with improvements in depression scores (CDRS-R, DIKJ).

WH 4b - Based on the study by Huan et al [52], we assume an inverse correlation between Omega-3 fatty acids and suicidal ideation (SIQ-Jr), in particular high levels of EPA will protect against suicidal ideation.

WH 4c – Based on the study by Beier et al [209] we assume that low Omega-3 fatty acids, in particular low EPA levels (and a low omega-3 index) will be associated with affect dysregulation, impulsivity/ emotionality (IES-27) and overall psychopathology.

WH 4d – Based on Kiecolt-Glaser et al [205], we hypothesize that high levels of overall stress (as measured with the PSS scale) will correlate with low levels of Omega-3 fatty acids, a pro-inflammatory state, increased saliva cortisol, and high levels of PUFAs oxidation products as

measured by F2 Isoprostanes in the urine and be inversely correlated with the Conner-Davidsons Resilience Scale.

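### The tests for WH3a, WH3c and the n-6/n-3 ratio of WH3b name no treatment-by-marker-by-time term, so they cannot separate prediction of omega-3 response from prognosis

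*Protocol*

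**What the plan says.** **Hypotheses (Protocol 5.2).** For WH3a, "we hypothesize that Omega-3 fatty acid response will be predicted by the ratio between pro- and anti-inflammatory markers". For WH3b, "those with an omega-3 index® <4 at baseline will benefit more from Omega-3 fatty acids treatment", with a further hypothesis that a high n-6/n-3 ratio goes with better response. For WH3c, low levels of EPA metabolites "will be a strong predictor of Omega-3 fatty acids response".

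**Analyses (Protocol 11.4.3).** The WH3a aim is worded as effect modification: "We will test the effect of inflammatory mediators on the efficacy of omega-3 treatment". The means is a single added factor, "by introducing an additional continuous factor (ratio between pro- and anti-inflammatory markers) into the linear regression model described in 11.4.2". For WH3b the plan is to compute the omega-3 index but to "introduce an additional binary factor (n-6/n-3 Omega ratio < 3 vs. n-6/n-3 Omega ratio > 5"). For WH3c it is "introducing additional continuous factors (levels of HETEs and E-series-resolvins at baseline) into the linear regression model".

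**Receiving model (Protocol 11.4.2).** It has "fixed effects for treatment, time (defined as the natural log of days since baseline + 1) and treatment-by-time interaction", plus random effects for participant and site. No marker appears in it.

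**SAP.** Section 7.1 enters omega-3 index and hsCRP as covariates. Section 7.1.1 then adds, as a separate step, an interaction of treatment, time and omega-3 index, judged by comparison with the simpler model. Section 2 leaves the other work on inflammatory and lipid markers and treatment response to future analysis plans.

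**The concern.** Whether a marker predicts response to omega-3 is a question about how the omega-3 minus placebo difference changes with the marker. The coefficient of a marker added as a factor answers a different question: whether CDRS-R differs by marker level, averaged over the arms. Followed as written, 11.4.3 would let a marker that merely tracks severity or course be read as an omega-3 response predictor.

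The protocol itself expects such a marker. WH4a in Protocol 5.2 proposes that severity is associated with a pro-inflammatory state, a higher omega-6/3 ratio and a lower omega-3 index. If WH4a is true, the added terms for WH3a and the n-6/n-3 ratio can be significant with no effect modification at all.

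Objective 3 of the trial is at stake, together with the rationale in Protocol 3.7 that markers should show who benefits and who does not. Protocol 11.4.3 and 11.4.6 also say that analyses not defined beforehand will be declared post hoc. If the interaction is not named in advance, the analysis that answers the question may carry that label while the misdirected one counts as pre-specified.

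**Working it through.** **1. The model as written.** Let T be treatment (0/1), t = ln(days + 1) and M the baseline marker.

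Mean CDRS-R = b0 + b1·T + b2·t + b3·T·t + g·M

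Treatment effect at time t = b1 + b3·t

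M drops out of the treatment effect, so by construction the effect is the same for every marker value. No result from this model can show effect modification. The coefficient g is the pooled marker association. Because t = ln(1) = 0 at day 0, the time scale implies that baseline CDRS-R is part of the response (SAP 7.1 states this for its own model). A severity association present before treatment therefore feeds into g.

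**2. The model the hypotheses need.** Add g2·M·t + g3·T·M + g4·T·M·t.

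Treatment effect at time t = b1 + b3·t + M·(g3 + g4·t)

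At t = 0 the marker-dependent part is g3, a baseline contrast whose expectation randomisation makes zero. Effect modification over follow-up is carried by g4. A marker-by-time term alone (g2) would still be prognostic.

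**3. The plan's own size.** Protocol 11.2 gives 108 per arm for 60% v 40% response, two-sided 0.05, 80% power, with continuity correction.
- Uncorrected: n = [1.96·√(2·0.5·0.5) + 0.842·√(0.24 + 0.24)]² / 0.2² ≈ 97 per arm, the figure in SAP 6.2.
- Corrected: (n/4)·[1 + √(1 + 4/(n·0.2))]² ≈ 107 per arm, within one of the stated 108.

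This is a main-effect size. The documents state no size or power for WH3a-c.

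**4. Behaviour of the two tests.** Simulation with N=220 (110 per arm), 4,000 runs, one endpoint, standard normal marker and error, and a treatment effect of -0.4 SD. The marker slopes are assumptions; the documents give none.

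| Marker | Slope, placebo | Slope, active | Added factor significant | Interaction significant |
|---|---|---|---|---|
| None | 0 | 0 | 5% | 5% |
| Prognostic only | +0.3 | +0.3 | 99% | 5% |
| Acts in active arm only | 0 | -0.4 | 81% | 82% |
| Crossover | +0.2 | -0.2 | 5% | 84% |

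Rows 2 and 3 are the point: a significant added factor does not tell prognosis from prediction.

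As a milder illustration, take a marker with assumed correlation r to a single CDRS-R endpoint and no effect modification. Fisher-z power is Φ(atanh(r)·√217 - 1.96): 61%, 85% and 96% for r = 0.15, 0.20 and 0.25.

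**5. Power of the interaction at N=220.** Normal approximation, one endpoint, two-sided 0.05, z-sum 1.96 + 0.842 = 2.80. Marker shares follow Protocol 5.2 (at least 50% with raised inflammatory markers, about 80% with low red-cell omega-3); the interaction sizes are assumptions.
- Binary marker with share q: SE² = 4/(N·q) + 4/(N·(1 - q)). For q = 0.5, SE = 0.270 and the detectable subgroup SMD difference is 2.80·0.270 ≈ 0.76. For q = 0.8, SE = 0.337 and it is 0.94.
- Continuous marker: SE = 2/√220 = 0.135 per SD, detectable 0.38 per SD.
- Power for a difference of 0.2, 0.4, 0.54 and 0.8: 11%, 32%, 52% and 84% (q = 0.5); 9%, 22%, 36% and 66% (q = 0.8). The main effect at SMD 0.4 has 84%.
- Total N for 80% power at a difference of 0.4: (4/q + 4/(1 - q))·(2.80/0.4)² = 785 (q = 0.5) or 1,227 (q = 0.8).

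**The case against.** **Part of this is already handled.** SAP 7.1.1 tests treatment x time x omega-3 index, which is the effect-modification test for the main WH3b hypothesis. This stands. A reader might infer that the plan has no such test for any marker, and the documents do not support that. The n-6/n-3 ratio that 11.4.3 actually enters remains uncovered.

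**The detail is deferred.** The SAP is later than the protocol and leaves the other markers to future plans, so 11.4.3 may be only an outline. This bears on where to correct the text, but it does not cure the problem: nothing in these documents replaces 11.4.3 for WH3a, WH3c or the ratio.

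**The protocol does not exclude an interaction.** That is true; it leaves the term unspecified. Yet the SAP treats entering a marker as a covariate and testing its interaction as two separate steps, so an added factor cannot be assumed to include the interaction.

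**True predictors would often still be flagged.** This also stands. A reader might infer that the written test would generally miss them. In the simulation that happens when effects cancel across the arms; a marker acting only in the active arm was flagged in 81% of trials. The hypotheses describe more benefit in some patients and little in others, not cancellation. The main fault is misattribution.

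**The percentages are not the plan's.** They rest on assumed slopes and correlations, one endpoint and complete marker data, whereas 11.4.2 is a repeated-measures joint model. They illustrate the mechanism and do not forecast error rates for this trial.

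**Conclusion.** The concern holds for WH3a, WH3c and the n-6/n-3 ratio of WH3b. For these, the stated analysis addresses prognosis while the hypotheses, and the stated WH3a aim, concern effect modification. It does not hold for the omega-3 index, which SAP 7.1.1 covers.

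The conclusion follows from the form of the model in steps 1 and 2 and depends on no assumed effect size. The rejection rates and interaction power are secondary and conditional on the stated assumptions. Marker data may also be fewer than 220, because Protocol 9.2.2.4 makes the additional bloods non-mandatory; that would lower power further.

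A reader might infer that the trial's efficacy conclusion is compromised. It is not: these are secondary marker analyses outside the primary report, and the primary CDRS-R result is unaffected. The point should be settled before the marker data are analysed.

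**What to change.** In Protocol 11.4.3, or in the follow-up plan that SAP section 2 announces, specify for WH3a, WH3c and the n-6/n-3 ratio:

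- Add treatment x marker x time with all lower-order terms, in the form already used in SAP 7.1.1.
- Base the test on the three-way term, or terms if time is a factor. Neither the marker main effect nor the baseline treatment x marker term should decide. If a model comparison is used, the simpler model must keep all lower-order terms.
- Report the omega-3 minus placebo difference with 95% CI across the marker range.
- Label the analyses exploratory and state the detectable interaction.

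In the same edit, reconcile the WH3b marker and cut-offs. The hypothesis uses omega-3 index <4 and >5; 11.4.3 enters the n-6/n-3 ratio at <3 v >5, which leaves values from 3 to 5 unassigned.

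The cost is about one paragraph and no new data. The downside is low power: at N=220 about 32% for an assumed subgroup difference of 0.4 SMD with a 50% share. That argues for estimates with intervals, not for keeping a test of a different question.
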